9.3.2. Eligibility Assessment

After consent has been obtained, subjects will be screened for study eligibility according to the Inclusion and Exclusion criteria. Subjects deemed eligible for participation in the study, as well as screen failures, will be entered in the subject Screening and Enrollment Log. Subjects previously randomized to PRESERFLO® MicroShunt, and who had the device explanted or another device implanted, will be considered to be eligible for enrollment in this study and will not be a screen failure. For those subjects displaying mental confusion and/or signs of significant dementia, the Principal Investigator should make a determination as to whether or not the subject is able to comply with all study requirements per Inclusion criterion #3.

9.3.3. Medical/Surgical History

An assessment of the subject's medical and surgical history will be performed at the Enrollment Visit and documented on the appropriate Case Report Form (CRF). This history will include ocular medical treatments and surgeries for both the study and fellow eye. The assessment will document all ocular medical treatments and surgical events, including medication changes, occurring in the time period between the completion of the last INN-005 visit i.e. Month 24, and enrollment in this study. Adverse events (AEs) that occurred during this time period, that have *resolved*, will be captured as part of the subject's medical/surgical history. Any AEs that are still *ongoing* at the time of consent will be documented as AEs and followed to resolution or study completion. Subjects with ongoing AEs at the time of study completion may exit the study if the Principal Investigator deems the subject to be stable. Any glaucoma reoperations occurring during this time period will be documented as part of the medical/surgical history and will also be captured by completing the Reoperation Form.

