9.1. Schedule of Events

	1	Schedul	e of Eve	nts					
					Foll	ow-Up E	valuati	on	
Activities	Enrol	lment ¹	Vi (Day	isit 1080 days)	Vi (Day	th 48 isit 1440 days)	Vi (Day	th 60 sit 1800 days)	Un- scheduled Visit
	SE	FE	SE	FE	SE	FE	SE	FE	
Study Assessments									
1. Informed Consent & Research Authorization	Х								
2. Eligibility Assessment	Х								SOC ⁴
3. Medical/Surgical History ²	X	X			S.				
4. Glaucoma Medications ^{3,5}	X	X	X	X	X	Х	X	X	
5. Concomitant (ocular) Medications ^{3,5}	X	X	X	X	X	X	X	X	
6. Adverse Event Assessment ⁵	X	X	Χ	X	Χ	X	X	X	
Study Procedures ⁶									
1. Manifest Refraction			X		X		X		
2. BCVA (ETDRS)			X		X		X		1
3. Visual Field			X		X		X		1
4. Slit Lamp Exam			X		X		X		
5. IOP			X		X		X		l
6. Pachymetry			X		X		X		
7. Anterior Segment OCT ⁷			X		X		X		
8. Endothelial Cell Density			X	X	X	X	X	X	SOC ⁴
9. Lens Status for Phakic Eyes ⁸			X		X		X		
10. Dilated Fundus Exam (incl. Vertical C/D Ratio)			X		X		X		
11. Bleb and Seidel Test			X		X		X		
12. Diplopia			X		X		X		
13. Motility			X		X		X		
14. Gonioscopy ⁹							X		

SE = Study Eye; FE = Fellow Eye

¹ Enrollment may occur at any time prior to the close of the follow-up window for the post-operative Month 60 Visit. Subjects who have passed the timepoints for the Month 36 or Month 48 Follow-Up Visits, prior to enrolling in the PRESERFLO® MicroShunt Extension Study, may still be enrolled to complete the remaining post-operative visit(s). No study-specific assessments, procedures, or data collection shall be performed prior to obtaining informed consent.

² Medical/Surgical events occurring between completion of the INN-005 study i.e. the Month 24 Visit and enrollment in the Extension Study, are retrospectively collected. Events that are ongoing at the time of consent will be documented as AEs.

³ The initial assessment at the time of enrollment includes only medications being taken at time of consent, and previously taken within 30 days of consent.

⁴ No study assessments are required at unscheduled visits, and subjects should be assessed per the institutional standard of care (SOC).

⁵ Adverse Events and medication changes occurring at any time throughout the duration of subject participation in the study shall be documented.

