Medications which have been re-started by the Investigator may be discontinued if in the Investigator's judgment the target IOP has been reached and the continued use of some or all of the therapy may not be required. Discontinuation of medications after re-introduction is recommended to be in the reverse order of re-introduction. The rationale for discontinuation will also be documented on the appropriate Follow-Up Visit Form by the Investigator. For medication discontinuation, the reason for the decision will be noted on the case report form such as IOP controlled, allergy to medication, or subject has undergone additional glaucoma surgery. A field for "Other" will be used to document any other reason for glaucoma medication discontinuation.

Another potential reason for intervention is an IOP below 6mmHg (hypotony). Interventions such as those indicated below should only be considered if the hypotony has caused or is likely to cause sequelae such as a flat chamber. No intervention is indicated when the vision is unchanged from the previous visit, there is no persistent choroidal detachment, the anterior chamber is not flat with lenscorneal touch, or the subject is asymptomatic. No intervention should be undertaken for hypotony which is not causing, or threatening to cause, a reduction in vision, as the intervention might cause procedure failure. These interventions should be documented as Adverse Events. Otherwise, the hypotony should be monitored with additional follow-ups as necessary.

- 1) Too loose or not enough sutures can result in hypotony that may be treated by adding more sutures in a separate surgical intervention (this action will be considered a failure).
- 2) Introduction of viscoelastic into the Anterior Chamber for the purpose of slowing aqueous flow and eliminating hypotony that is causing a reduction of best corrected visual acuity (two or more lines) or causing the presence of persistent choroidal detachment (3 or more months if peripheral, up to one month if kissing), or causing hypotony maculopathy (also documented on the Adverse Event Form as the action taken for an event.)

12. Adverse Events

An adverse event is any symptom, sign, illness, or experience, which develops or worsens during the course of the study, and which may or may not be considered device and/or procedure related.

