An Unanticipated Adverse Device Effect (UADE) is defined as any serious adverse effect on the health or safety or any life-threatening problem or death caused by, or associated with, a device, if that effect, problem, or death was not previously identified in nature, severity, or degree of incidence in the investigational plan or application (including a supplementary plan or application), or any other unanticipated serious problem associated with a device that relates to the rights, safety, or welfare of subjects.

13. Assessment of Safety

Adverse Events will be collected for all enrolled subjects beginning at the Enrollment (Screening) Visit until the subject completes the study. The Principal Investigator is responsible for ensuring that all adverse events observed by the Investigator or site staff, or reported by subjects, are properly captured and recorded on the Adverse Event Form.

ENROLLMENT:

All SAEs that occurred between the Month 24 Visit of the INN-005 study and the time of consent for the INN-005-EXT study, are still *ongoing* at the time of consent, and for which surgery, physical intervention, or medication changes was required, whether they are considered to be device- or procedure-related or not, will be documented as AEs at the Enrollment Visit.

All ocular AEs, for both the study and fellow eye, that occurred between the Month 24 Visit and the time of consent, that are still *ongoing* at the time of consent, and for which surgery, physical intervention, or medication changes was required, will be documented as AEs at the Enrollment Visit.

All SAEs and ocular AEs that occurred between the Month 24 Visit and the time of consent, for which, surgery, physical intervention, or medication changes was required, and which are *resolved* at the time of consent, shall be captured in the subject's Medical/Surgical history at the Enrollment Visit.

If the action taken to address an ongoing AE at the time of consent was to administer medication more than 30 days prior to consent, the concomitant medication should be recorded on the CRF.

FOLLOW-UP:

All SAEs occurring during the study from the time of consent for the INN-005-EXT study will be assessed at each of the follow-up visits. SAEs, whether they are considered to be device- or procedure-related or not, must be documented.

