9. SAFETY ANALYSES

9.1. Safety-Related Definitions

9.1.1. Adverse Event

Under Protocol INN-005-EXT Section 12, an adverse event (AE) is any untoward medical occurrence, unintended disease or injury, or untoward clinical signs (including abnormal laboratory findings) in subjects, users or other persons, whether or not related to the investigational medical device or procedure. Any ocular AE that occurred prior to but is still ongoing at the time of consent or occur at any time after the date of informed consent through the last study visit will be collected for the INN-005-EXT study. Non-ocular serious adverse events (SAEs), whose definition is listed below, will also be collected; however, non-ocular non-serious adverse events will not be collected.

The severity of each AE will be graded by the Principal Investigator as Mild, Moderate, or Severe. AEs will also be rated by the Investigator as to their causality/relationship to the study procedure and to the study device.

Each AE will be mapped into a coded term by a Santen Clinical Scientist based on a review of all AE description records before the database lock.

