9.2.2. Analysis of Secondary Safety Outcome Measures

9.2.2.1. Adverse Events

Subjects with any ocular AEs, SAEs, and UADEs will be tabulated and summarized by type of AEs for each study group. Ocular AE summaries (i.e., the number and percentage of subjects reporting to at least one AE) will also be provided for ocular AEs judged to be device- or procedure-related.

AEs, SAEs, and UADEs, if any, will be listed separately.

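### SAP 9.1.1 sets no onset limit for ocular AEs ongoing at consent, against Protocol 13, so unresolved INN-005 events can enter the extension's ocular AE incidence

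*Protocol*

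**What the plan says.** **Protocol 13 (Assessment of Safety, Enrollment)** sets two conditions for an ocular event already present at consent. The first is a period of onset: "All ocular AEs, for both the study and fellow eye, that occurred between the Month 24 Visit and the time of consent". The second is that the event is ongoing "and for which surgery, physical intervention, or medication changes was required, will be documented as AEs at the Enrollment Visit". The paragraph on SAEs in the same section carries the same two conditions.

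**Protocol 9.3.3** deals with medical and surgical history between Month 24 and enrollment. Resolved events go to history: "Adverse events (AEs) that occurred during this time period, that have" resolved. The next sentence says that any AEs still ongoing "at the time of consent will be documented as AEs and followed to resolution or study completion". That sentence does not repeat the period and names no intervention condition.

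**Protocol 9.1, footnote 2**, gives the same rule with the period stated: "Medical/Surgical events occurring between completion of the INN-005 study i.e. the Month 24 Visit and enrollment in the Extension Study, are retrospectively collected". Those that are ongoing at consent become AEs. Footnote b to SAP Table 1 says the same.

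**Protocol 12** opens by describing an AE as something "which develops or worsens during the course of the study".

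**SAP 9.1.1** defines what is collected: "Any ocular AE that occurred prior to but is still ongoing at the time of consent", together with ocular AEs that arise after consent. It gives no earliest onset and no intervention condition.

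**SAP 9.2.2.1** gives the analysis: "Subjects with any ocular AEs, SAEs, and UADEs will be tabulated and summarized by type of AEs for each study group". It states no onset filter.

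**The concern.** Incidence of ocular AEs in the study eye is a listed secondary safety outcome (Protocol 4.2, SAP 2.2.2) in a study whose purpose is safety in years 3 to 5. INN-005 collected all AEs (Protocol 3.1). A chronic event that began there and never resolved, such as ptosis or cataract progression from the list in Protocol 13.2, should already be on record in that study. SAP 9.1.1, read literally, takes it into the extension as well, and nothing in SAP 9.2.2.1 takes it out again.

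The table would then mix two quantities: events that arose after Month 24, and the stock of unresolved events left from years 0 to 2. An arm with more unresolved early complications could look worse in the extension even if new events were equally common in both arms. That there are no hypothesis tests does not remove the problem, because the descriptive table is itself the result.

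**Working it through.** **1. The rules side by side.** For an ocular AE that began before consent and is ongoing at consent:

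| Source | Onset limit | Intervention condition |
|---|---|---|
| Protocol 13 | After the INN-005 Month 24 Visit | Yes |
| Protocol 9.1, footnote 2; SAP Table 1, footnote b | Month 24 Visit to enrollment | No |
| Protocol 9.3.3 | Not repeated; the context implies Month 24 to enrollment | No |
| SAP 9.1.1 | None | No |
| SAP 9.2.2.1 (table) | None | No |

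SAP 9.1.1 stands alone on onset. On the intervention condition, Protocol 13 stands alone.

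**2. One event traced through.** Take an ocular AE that began during INN-005 and is stable and unresolved at consent. Under Protocol 13 it is not entered at enrollment. Under SAP 9.1.1 it is. If it reaches the database, SAP 9.2.2.1 counts the subject.

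**3. Do the SAP Table 2 windows catch it?** Table 2 uses 30-day months: 1080/36 = 1440/48 = 1800/60 = 30. Month 24 is therefore Day 24 × 30 = 720. The first post-operative window for AEs opens at Day 781, which is 781 − 720 = 61 days later. The windows then run without gaps (1170 to 1171, 1530 to 1531).

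- If AEs are placed by onset day, an event with onset on Day 780 or earlier falls in no Month 36, 48 or 60 window. The by-visit incidence of sight-threatening AEs (SAP 9.2.1, the primary outcome) would then leave it out.
- SAP 9.2.2.1 names no window, so the overall ocular AE table has no such screen.
- SAP 4.3 does not say outright that placement is by onset day. Reading Day 780 as the close of the INN-005 Month 24 window is likewise an assumption drawn from Table 2. A fixed Day 781 is also not each subject's own Month 24 Visit date, so Table 2 cannot stand in for an onset filter.

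**4. Illustration of size.** The documents give no AE rates, so both inputs are assumed. Let p1 be the share of subjects with a new ocular AE and p0 the share carrying an unresolved INN-005 ocular AE, independent of each other. The tabulated share is

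1 − (1 − p0)(1 − p1) = p1 + p0(1 − p1).

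| p1 | p0 = 2% | p0 = 5% | p0 = 10% | p0 = 20% |
|---|---|---|---|---|
| 10% | 11.8% | 14.5% | 19.0% | 28.0% |
| 30% | 31.4% | 33.5% | 37.0% | 44.0% |
| 50% | 51.0% | 52.5% | 55.0% | 60.0% |

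For example, 0.30 + 0.05 × 0.70 = 0.335 and 0.30 + 0.20 × 0.70 = 0.44.

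If p1 = 30% in both arms and p0 is 20% in one and 30% in the other, the table would show 44% against 0.30 + 0.30 × 0.70 = 51%. The gap of 7 points is the assumed 10-point difference in p0 times 0.70. It shows how the effect works and does not estimate it.

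**The case against.** The strongest reply is that the protocol governs collection and Protocol 13 already sets the limit. A site that follows it enters no INN-005-onset event at enrollment, so there is nothing for the SAP to count. Footnote b to SAP Table 1 repeats the Month 24-to-enrollment period, and SAP 7.3 uses it for history. On this view SAP 9.1.1 is loosely worded and no more. That argument has force on likelihood. It does not settle the matter, because SAP 9.1.1 is the SAP's own statement of which AEs are in scope, it contradicts Protocol 13, and the table has no second safeguard.

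Several stronger readings are tempting and are not supported:

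- **That Protocol 9.3.3 records every ongoing AE whatever its onset.** The paragraph is about Month 24 to enrollment, and the sentence pairs ongoing events with the resolved events of that period. It is ambiguous at most.
- **That Protocol 12 rules these events out.** Its opening line points that way, but the same section gives a formal definition with no time limit, and SAP 9.1.1 reproduces that one. Taken strictly, the opening line could also exclude the Month 24-to-consent events that Protocol 13 admits.
- **That INN-005 events are counted again as new.** Nothing labels them new, and the date of onset is recorded for every AE (Protocol 14.1).
- **That joining the two studies counts an event twice.** Protocol 21 says only that the data may be continuous with INN-005. No pooled AE table is planned, and counts are of subjects.
- **That the primary safety outcome is distorted.** Placement by onset day would largely shield it, as shown above.

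It is also fair to say that the study is descriptive, with no labeling claims intended, and that how INN-005 closed AEs unresolved at Month 24 cannot be seen from these documents.

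**Conclusion.** The point holds in limited form. SAP 9.1.1 lacks both the onset limit and the intervention condition of Protocol 13. Protocol 9.3.3 is ambiguous on the first and lacks the second. Because SAP 9.2.2.1 applies no onset filter, an unresolved INN-005 ocular AE can be counted in the extension's ocular AE incidence, which would then be part prevalence and part incidence.

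Whether this happens depends on which rule sites and programmers follow. Its size depends on how many INN-005 ocular AEs were unresolved at consent, which the documents do not give. The range of 33.5% to 44% against a true 30% rests on assumed carry-over of 5% to 20% and on independence. A reader might infer a real spurious difference between arms from the 7-point example; the documents give no rates by arm, so no such difference can be claimed. The change is worth making because it is cheap and settles the meaning of a listed outcome.

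**What to change.** 1. Align SAP 9.1.1 and Protocol 9.3.3 with Protocol 13, stating in each the same onset period (after the subject's INN-005 Month 24 Visit and before consent) and the same intervention condition. Bring footnote 2 of the Protocol schedule and footnote b of SAP Table 1 into line.
2. In SAP 9.2.2.1, restrict the ocular AE incidence tables to events with onset, or worsening, after the subject's INN-005 Month 24 Visit. Use the visit date itself, not Day 781.
3. Flag any INN-005 event that is carried over and list these separately by arm, outside the incidence tables, so that no safety information is lost.

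The cost is one derivation rule and a flag. Onset dates are already recorded and subject IDs are unchanged from INN-005 (Protocol 8.2), so no new data are needed. Reported ocular AE counts may fall slightly.

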9.3.4. Glaucoma Medications

A glaucoma medications assessment will be performed at the Enrollment Visit and documented on the appropriate CRF for the duration of the study. This assessment will include medications for both the study and fellow eye. Only glaucoma medications taken at the time of consent, and those taken within 30 days of consent, are required to be collected. If the action taken to address an ongoing AE was to administer glaucoma medication more than 30 days prior to consent, the medication should be recorded on the appropriate CRF. Each ocular hypotensive medication will be recorded on the CRF.

9.3.5. Concomitant (Ocular) Medications

An ocular medication and supplements (including vitamins) assessment will be performed at the Enrollment Visit and documented on the appropriate CRF for the duration of the study. This assessment will include medications for both the study and fellow eye. Only medications taken at the time of consent, and those taken within 30 days of consent, are required to be collected. If the action taken to address an ongoing AE was to administer medication more than 30 days prior to consent, the concomitant medication should be recorded on the appropriate CRF.

9.3.6. Adverse Events Assessment

The Investigator or site staff will determine whether any AEs have occurred. Subjects should be encouraged during this assessment to report ocular AEs spontaneously or in response to general, non-directed questions. At any time during the study, the subject may volunteer information that resembles an AE. For subject-reported AEs, as much information as possible should be obtained, including all required treatments and outcomes of the AE.

An adverse event assessment will be performed as part of the Enrollment Visit, and at each of the Follow-Up Visits.

9.4. Study Procedures

Most of the study procedures are the same as those performed as part of the INN-005 study, as outlined in section 3.1. The only differences are the following:

Study Assessment*	INN-005 Study ¹ (Month 12 and 24)	INN-005-EXT Study ² (Month 36, 48, and 60)	Comments
IOP	Diurnal	Standard	INN-005: Diurnal IOP INN-005-EXT: Standard IOP
Anterior Segment OCT	Not performed	Performed	Added to INN-005-EXT as an optional assessment to further assess position of PRESERFLO® MicroShunt along with slit lamp examination; Only performed for subjects with device still implanted
Adverse Event Assessment	All AEs	All SAEs; Ocular AEs	INN-005: All AEs collected INN-005-EXT: All ocular AEs in study & fellow eye and all SAEs will be

			collected. Non-serious, non-ocular AEs will not be collected.
Ocular QOL Questionnaire	X		Not included in INN-005-EXT
General Health Questionnaire	X		Not included in INN-005-EXT
Gonioscopy	х	X (Month 60) ³	Added to INN-005-EXT to further assess position of PRESERFLO® MicroShunt; Only performed for subjects with device still implanted

³Only applies to MicroShunt subjects who agree to this assessment by signing the Informed Consent Addendum.

The following background information regarding the performance of some of the required study procedures is provided to assist with appropriate follow-up for all subjects in this study:

9.4.1. BCVA (ETDRS)

Best Corrected Visual Acuity (BCVA) should be measured using Early Treatment of Diabetic Retinopathy Study (ETDRS) charts at 4 meters (13 feet and 1.5 inches, or 157.5 inches) in both eyes and reported in LogMAR units.

Visual acuity testing should precede slit lamp examination, intraocular pressure measurement, the administration of topical anesthetic agents, or any examination requiring contact with the anterior segment.

The visual acuity chart must be retro-illuminated ("back-lit"). The standard chart requires a distance from subject to chart of 4 meters. Ideally, the subject should be seated. Sites should refer to the instructions on the commercial ETDRS charts and the Visual Acuity Testing Manual, provided as part of the INN-005 study.

The subject should attempt to read each letter, line by line, left to right, beginning with line 1 at the top of the chart (20/200 line). The subjects should be told that the chart has letters only, no numbers. If the subject reads a number, he or she should be reminded that the chart contains no numbers, and the examiner should then request a letter in lieu of the number. The subjects should be asked to read slowly, about one letter per second, so as to achieve the best identification of each letter. He/she is not to proceed to the next letter until he/she has given a definite response.

In order to provide standardized and well-controlled assessment of visual acuity during the study, all visual acuity assessments for a subject must be performed consistently (e.g., the same lighting conditions, viewing distance, etc.) during the entire study.

The following steps will be used for LogMAR scoring:

- 1. The examiner records each letter identified correctly by circling the corresponding letter on the Distance Visual Acuity Worksheet to be provided to the investigative sites.
- 2. Letters read incorrectly or not read at all are not marked on the form.
- 3. Each letter read correctly is scored as one point.
- 4. The total score for each eye is recorded on the worksheet after testing is completed.

